- **1. Source of Population:** (a) ILL Participant Yes No (b) Non ILL Participant Yes No Yes No (c) Minors or persons under guardianship 2. Does the study involve? (a) Physical risks Yes No To the subjects No (b) Social Risks Yes No Psychological Yes (c) Risks to subjects (d) Discomfort to Yes No Subjects No (e) Invasion of the body Yes Invasion of Privacy Yes No (f) Yes (g) Disclosure of No Information damaging to Subject or others 3. Does the study involve? (a) Use of records, Yes No (Hospital, medical, Death, birth or other) (b) Use of fetal tissue No Yes Or abortus No
 - (c) Use of organs or Yes (N Body fluids

4. Are subjects clearly informed about?

(a)	Nature and purposes of study	Yes	No
(b)	Procedures to be followed including alternatives used	N/A	
(c)	Physical risks	N/A	
(d)	Private questions	Yes	No
(e)	Invasion of the Body	N/A	
(f)	Benefits to be Derived	Yes	No
(g)	Right to refuse to participate or to withdraw from st	Yes	No
(h)	Confidential handling of data	Yes	No
(i)	Compensation where there are risks	N/A s or	

- (1) Compensation N/A where there are risks or loss of working time or privacy is involved in any particular procedure
- 5. Will signed consent form/verbal consent be required?
- (a) From Subjects Yes No
 (b) From parent or guardian (if subjects are minors)
 6. Will precautions be Yes No
 - taken to protect anonymity of subjects

RESEARCH PROTOCOL

• **Project Title:** Development and Evaluation of an Artificial Intelligence Model for Bone Mineral Density Prediction from X-Ray Images

Summary: Osteoporosis, a pervasive skeletal disorder characterized by diminished bone strength predisposing individuals to an increased risk of fractures, presents a substantial public health challenge globally [1][2]. It's estimated that osteoporosis and its consequent increase in fracture risk significantly contribute to morbidity, mortality, and economic costs [3][4]. Despite the availability of effective treatments, the condition often remains undiagnosed and untreated until a fracture occurs, underscoring the critical need for early detection and intervention [5][6].

Dual-energy X-ray absorptiometry (DEXA) is the gold standard for assessing bone mineral density (BMD) and fracture risk [7]. However, its utility is hampered by limited availability, especially in rural and low-resource settings, such as Bangladesh, where osteoporosis prevalence is notably high [8]. The scarcity of DEXA units exacerbates the challenge of osteoporosis screening and management, leaving a significant portion of the population at risk [9].

In this context, plain X-ray imaging, widely available even in resourceconstrained settings, emerges as a promising alternative for osteoporosis screening. Recent advancements in deep learning and computer vision offer the potential to automate the analysis of X-ray images for BMD estimation. The objective of this thesis is to develop and evaluate an Artificial Intelligence (AI)-based model that predicts BMD from plain X-ray images of the lumbar spine and pelvis. By leveraging Convolutional Neural Networks (CNNs), this model aims to identify individuals at risk of osteoporosis and osteopenic conditions without the need for DEXA. The proposed AI model processes X-ray images to detect subtle changes in bone texture and density, potentially offering a rapid, non-invasive, and cost-effective tool for largescale osteoporosis screening, particularly beneficial in regions like Bangladesh where DEXA is scarcely available. This research addresses the critical gap in osteoporosis screening and diagnosis, aiming to contribute significantly to public health by enabling earlier detection and management of osteoporosis, thereby reducing the incidence of fractures and associated healthcare costs [10].

• Introduction: Globally, osteoporosis poses a significant public health challenge, with an estimated 200 million patients affected worldwide and about it is responsible for nearly 9 million fractures annually, indicating its profound impact on morbidity, mortality, and healthcare costs [11]. In Bangladesh, the prevalence of osteoporosis is concerning, with a study revealing that among a cohort of 526 individuals, 37.3% are at risk of developing the condition [8]. The risk is notably higher in females (43.2%) compared to males (30.3%) and escalates with age, particularly after 50 years, reflecting global trends. Furthermore, the presence of diabetes and cardiovascular diseases significantly increases the risk, with a striking 78% of cardiovascular patients being at risk. Notably, individuals with multimorbidity present an even higher prevalence rate of 90%. This underlines an urgent need for effective screening and early detection strategies to mitigate the burden of osteoporosis, especially in resource-constrained settings.

Recent advancements in deep learning, particularly deep learning, have shown promise in utilizing plain radiographs for BMD prediction, potentially bypassing the need for more expensive and less accessible DEXA scans [12][13]. Studies leveraging CNNs have been successful in extracting clinically relevant features from X-ray images to predict BMD and assess fracture risk, demonstrating AI's potential in osteoporosis screening [14].

Despite these advancements, the application of AI in osteoporosis diagnosis faces challenges, notably the generalizability of models across diverse populations and healthcare settings. Most existing studies utilize datasets from localized patient populations and are often limited by the availability and quality of annotated data. This raises concerns about the models' performance and applicability in different regions, particularly in low- and middle-income countries where the disease burden is highest, and healthcare resources are scarce.

To address these gaps, our research aims to develop and evaluate an AI model for BMD prediction from X-ray images, with a particular focus on enhancing model generalizability and diagnostic accuracy. We intend to collect a comprehensive dataset comprising X-ray images, BMD measurements from local healthcare facilities. This diverse dataset will enable us to train and validate AI models that can robustly predict osteoporosis across different patient populations.

Our goal is to create an AI-assisted diagnostic tool that can be easily integrated into clinical workflows, offering a cost-effective and accessible solution for osteoporosis screening.

• **Objectives:** The primary objective is to curate a comprehensive dataset of X-ray images sourced from publicly available domains and local health facilities, encompassing a diverse representation of patient demographics, geographic locations, and equipment variations. Building upon this dataset, we seek to develop a robust artificial intelligence model capable of prediction of bone mineral density from X-ray images.

The specific objectives of the study are:

- a) To develop a deep learning convolutional neural network (CNN) model that can accurately predict Bone Mineral Density (BMD) values from Xray images, using both prospective and retrospective data collection methods.
- b) To validate the AI model's performance on a diverse dataset encompassing a broad demographic, including variables such as age, gender, height, weight, menopausal status, and the presence of comorbidities like cardiovascular disease and diabetes.
- c) To evaluate the model's performance using a range of metrics, including Area Under the Precision-Recall Curve (AUPRC), accuracy, Mean Absolute Error (MAE), and Pearson Correlation Coefficient (PCC), ensuring its robustness in predicting BMD.
- d) To assess the usability and interpretability of the AI model's output by healthcare professionals, determining its integration into clinical practice and its impact on the diagnostic workflow efficiency.
- e) To measure the generalizability and adaptability of the model across various healthcare settings, ensuring the AI system's reliability on X-ray images from different populations and regions.

- f) To investigate the model's potential in enhancing early detection and treatment planning for osteoporosis by providing a non-invasive, cost-effective tool for BMD estimation, potentially leading to better patient management and outcomes.
- g) To assess the AI model's role as a decision support tool in determining the necessity for additional diagnostic procedures, such as DEXA scans, thereby optimizing patient care pathways and potentially reducing healthcare costs.
- **Rationale:** The early detection and treatment of osteoporosis are crucial in preventing fractures and ensuring the quality of life for individuals at risk. However, in developing countries like Bangladesh, the standard method for assessing bone health, DEXA, is not widely accessible due to its cost and the scarcity of specialized equipment and trained personnel. Consequently, many cases of osteoporosis remain undiagnosed until a fracture occurs, which significantly impacts patient outcomes and healthcare costs.

The current pathway for osteoporosis suspicion in Bangladesh typically begins with an X-ray prompted by symptoms of pain or fracture. If osteoporosis is suspected, a subsequent BMD test is recommended. This twostep process not only increases the financial burden on patients but also delays the diagnosis and treatment of osteoporosis, especially in rural areas where BMD testing facilities are scarce.

Addressing these challenges, our research proposes the use of deep learning algorithms to predict BMD values directly from X-ray images, which are more readily available and cost-effective than DEXA scans. By training a CNN with a dataset that includes demographic and clinical covariates, such as age, gender, menopausal status, cardiovascular disease, and diabetes, our AI model aims to identify correlations that can accurately predict BMD [15]. In this way, the developed AI model is intended to function as an assistive tool, providing a preliminary assessment to guide physicians on whether a more expensive and resource-intensive DEXA scan is warranted. This approach could substantially streamline the diagnostic process, making it more efficient and potentially reducing unnecessary medical expenses for patients.

- **Methodology:** In our data-driven approach to developing a predictive model for Bone Mineral Density (BMD) from X-ray images, we will collect and utilize a comprehensive dataset that includes X-ray images and BMD reports alongside demographic and clinical details of the subjects. The methodology will ensure patient privacy and data security, with all personally identifiable information being excluded from the dataset.
 - a) **Study Population:** The study is structured as a prospective and retrospective investigation aimed at developing and evaluating an AI-based diagnostic tool for the prediction of BMD from X-ray image analysis. The population will include subjects with varying bone densities as determined by DEXA scans, which serve as the gold standard for BMD measurement. The study will target a diverse demographic to account for the variability in bone health across different ages, genders, and clinical backgrounds.

Inclusion criteria:

- Subjects of any gender and age group (18 and above) for whom X-ray imaging of relevant skeletal sites (e.g., spine, hip) is available.
- Individuals willing to participate and who have provided informed consent for the use of their X-ray images and clinical data for research purposes.
- Subjects with both X-ray images and DEXA scan results.
- Accessibility to supplementary medical records that may contribute to the model's predictive accuracy, such as historical data on fractures, calcium levels, and other osteoporosis-related factors.

Exclusion criteria:

- Subjects for whom X-ray images or clinical data are incomplete or of insufficient quality for analysis.
- Individuals with medical conditions that could significantly alter bone density independently of osteoporosis, such as bone cancers or certain metabolic diseases.
- Subjects who have undergone treatments or procedures that might significantly impact bone density measurement, such as long-term steroid use or recent orthopedic surgeries.
- Pregnant women, given the potential impact on screening results and the need for special considerations during pregnancy.
- b) **Sample size calculation:** Following the methodology of sample size calculation to evaluate diagnostic performance (for algorithms in this case), we use the following method of calculation for a target sensitivity and specificity incorporating disease prevalence [16]:

$$N_{sen} \ge \frac{Z^{2}_{(1-\alpha)/2} \times sen (1-sen)}{c^{2} \times p}$$

$$N_{spec} \ge \frac{Z^{2}_{(1-\alpha)/2} \times spec (1 - spec)}{c^{2} \times (1 - p)}$$

Where,

N _{sen}	=	Required sample size for sensitivity, sen
N_{spec}	=	Required sample size for specificity, spec
α	=	Confidence level
$Z^{2}_{(1-\alpha)/2}$	=	The Z -score for the confidence level α
p	=	Prevalence of osteoporosis
С	=	Precision
sen	_	
sen	=	Estimated sensitivity
spec	=	Estimated specificity

The final sample size N is calculated based on the larger of the two values N_{sen} and N_{spec} . In this study, as we are using deep learning techniques, we need the medical image samples to reflect the various osteoporosis, osteopenia and normal cases. For our analysis, we assume an 95% confidence level, precision of 0.05, and prevalence of osteoporosis, p = 0.373 [8]. We estimate the sensitivity and specificity of our algorithms to be at 91.1% and 68.9% respectively (*sen* = 0.911 and *spec* = 0.689) [17]. Using these values, we obtain the sample size values: $N_{sen} = 335$ and $N_{spec} = 526$. Since $N_{spec} > N_{sen}$, the final sample size for the study will be:

$$N = N_{sen} = 526$$

We can set a target of N = 600.

c) **Procedures:** In the prospective phase of the study, data collection will be conducted within clinical settings. Eligible patients will be approached during X-ray scans and BMD tests and presented with a consent form for their consideration. Upon agreement, a unique identifier will be assigned to maintain data integrity while preserving patient anonymity. Following the consent process, patients will provide essential clinical information. Healthcare professionals will perform an X-ray or DEXA scan, and the results will be generated and collected. This approach ensures the acquisition of non-identifiable information, unique data identifiers, and informed consent directly within the clinical setting, aligning with the specific requirements of the study.

In the retrospective phase of the study, additional data will be extracted from the clinic's database. We will collect all spine and hip X-ray images and BMD reports from the radiology department. The identification and matching process will rely on patient ID, phone number, date of birth, and other shared clinical information present in both the X-ray and BMD reports. Given the retrospective nature of this approach, tracking down and obtaining consent from individual patients is not feasible. To address privacy concerns, any personally identifiable patient information will be systematically removed from the collected data. This strategy ensures compliance with privacy standards while utilizing valuable information from previous screenings. Although informed consent cannot be obtained for this specific dataset, the study will strictly adhere to ethical guidelines and prioritize patient privacy throughout the data extraction process from the clinic's database.

- d) **Methods of Data Collection:** The following fields will be recorded in the data collection for this study:
 - Patient ID (unique identification number)
 - Date & time of the data input
 - Age
 - Gender
 - Phone number
 - X-ray image (hip or spine)

- DEXA scan result
- BMI
- Menopausal status
- Diabetes
- Cardiovascular disease and other clinical covariates

The X-ray images, and DEXA scan result of the subjects along with the relevant clinical covariates will be used to design the algorithms. The standard test status and the corresponding result will be used as the ground truth for our detection algorithm.

e) **Data Interpretation:** Upon the conclusion of data collection, exploratory data analysis to assess the distribution of patients across different demographics and clinical factors, including age, gender, menopausal status, presence of cardiovascular diseases, diabetes, and their correlation with BMD values. This process will ensure a comprehensive understanding of the dataset's characteristics and the establishment of a balanced dataset that represents a wide spectrum of patient profiles.

The refined dataset will serve as the foundation for training and evaluating our AI model, specifically designed for the regressionbased prediction of BMD from X-ray images. Our AI algorithm will leverage CNN to process X-ray images and predict BMD values, aiming to identify potential cases of osteopenia, osteoporosis, and normal.

To ascertain the model's performance and its clinical applicability, we will compare the AI-generated predictions with actual BMD measurements obtained from DEXA scans. This validation process will involve collaboration with orthopedic specialists and radiologists who will review the AI predictions in the context of their clinical experience and available patient information.

f) Statistical Analysis: Upon finalizing the dataset, our statistical analysis will concentrate on evaluating the artificial intelligence model's capability to predict BMD from X-ray images accurately. Performance metrics such as Mean Absolute Error (MAE), Pearson Correlation Coefficient (PCC), Area Under the Precision-Recall Curve (AUPRC), and accuracy will be employed to meticulously assess the model's performance. To ensure the reliability of our findings, we will implement k-fold cross-validation techniques, providing a framework for evaluating our model across various subsets of data. This approach will allow us to calculate mean values and standard deviations for each performance metric, offering a comprehensive understanding of the model's predictive accuracy and consistency. The culmination of our analysis will involve a comparative review of different CNN architectures and training methodologies to determine the most effective strategy for BMD prediction from X-ray images.

Utilization of Results: The study results will play a crucial role in the development and evaluation of an automatic BMD prediction algorithm for osteoporosis screening. The algorithm's primary objectives are:

a) BMD Prediction: To accurately predict BMD values from X-ray images, facilitating an automated assessment tool for early detection of osteoporosis and osteopenia. This tool aims to bridge the gap in accessibility to BMD testing, especially in resource-limited settings.

b) Clinical Decision Support: To aid healthcare professionals by providing automated BMD assessments, enhancing their ability to make informed decisions regarding patient care. The model's predictions can help prioritize patients who need further testing or intervention, streamlining the diagnostic process.

c) Correlation Analysis: To explore and identify significant relationships between BMD or osteoporosis and collected clinical covariates such as age, gender, menopausal status, cardiovascular diseases, and diabetes. This analysis aims to enhance understanding of the factors influencing bone health, contributing to personalized and more precise osteoporosis risk assessment and management strategies.

d) Data Management for Bone Health Research: To enable systematic storage and organization of X-ray images along with their corresponding BMD values and clinical data. This will not only support future research in the field of bone health but also ensure the privacy and security of patient data throughout the process.

These outcomes are poised to significantly enhance the efficiency and accuracy of osteoporosis screening, providing valuable support to healthcare professionals in Bangladesh.

- **Facilities:** For the collection of data for our thesis on predicting Bone Mineral Density (BMD) from X-ray images, no extra facilities are necessary beyond those already available in the radiology departments (e.g., X-ray imaging, DEXA scan, and data storage capabilities).
- Approval / Forwarding of the Head of Department / Institute / IRB: A forwarding letter from the Department of Biomedical Engineering, Bangladesh University of Engineering and Technology (BUET) is attached.
- **Flow Chart:** The data collection activity and the corresponding timeline is described in the Gantt chart below:

No.	Work/Activities	Months			
		1	2	3	4
1	Initial algorithm with publicly available data				
2	Collection of images, reports and metadata				
3	Homogenization and organization of data				
3	Data processing and analysis				

- Ethical Implications: The proposed retrospective/prospective study based on medical records is designed to develop and evaluate the diagnostic performance of AI algorithms that will predict BMD from X-ray images. The study poses minimal to no risk to the subjects according to the HHS (USA) definition.
- References:
 - O. Johnell and J. A. Kanis, "An estimate of the worldwide prevalence and disability associated with osteoporotic fractures," Osteoporos. Int., vol. 17, no. 12, pp. 1726–1733, Dec. 2006, doi: 10.1007/s00198-006-0172-4.
 - L. Sànchez-Riera et al., "The global burden attributable to low bone mineral density," Ann. Rheum. Dis., vol. 73, no. 9, pp. 1635–1645, Sep. 2014, doi: 10.1136/annrheumdis-2013-204320.
 - A. S. Nazrun, M. N. Tzar, S. A. Mokhtar, and I. N. Mohamed, "A systematic review of the outcomes of osteoporotic fracture patients after hospital discharge: morbidity, subsequent fractures, and mortality," Ther. Clin. Risk Manag., vol. 10, pp. 937–948, Nov. 2014, doi: 10.2147/TCRM.S72456.

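### Hip and spine X-rays share one model, a DEXA field with no skeletal site and one metric list, so a correlation taken over both regions can exceed the within-region value

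*Protocol*

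**What the plan says.** The Protocol's Summary describes a single model that "predicts BMD from plain X-ray images of the lumbar spine and pelvis". Methodology a) admits subjects for whom "X-ray imaging of relevant skeletal sites (e.g., spine, hip) is available" and sets no quota per site. In Methodology d) the image field reads "X-ray image (hip or spine"), and the next field is a DEXA scan result with no skeletal site attached. Methodology c) matches retrospective X-rays to BMD reports by patient ID, phone number, date of birth and other shared clinical information; the region is not named as a matching item.

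Methodology f) gives one list, beginning "Performance metrics such as Mean Absolute Error (MAE), Pearson Correlation Coefficient (PCC") and continuing with AUPRC and accuracy. Each metric is to be summarised by a mean and a standard deviation over cross-validation folds. Region is not mentioned.

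Methodology b) derives one sample size. Its inputs are given as "we assume an 95% confidence level, precision of 0.05, and prevalence of osteoporosis, p = 0.373", with "sensitivity and specificity of our algorithms to be at 91.1% and 68.9% respectively". The two component sizes are 335 and 526, and the section ends with "We can set a target of N = 600". No split between hip and spine is given.

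**The concern.** A correlation over a mixture of two groups has two sources: how well predictions follow patients within a group, and how far apart the group means lie. If mean BMD differs between hip and spine, a network that can tell the two views apart gains correlation from the anatomy alone. That part has no value to a clinician, who already knows which region was imaged. PCC and MAE are the two metrics on the list that address the regression task directly, and Methodology f) also ends in a comparison of CNN architectures. An inflated PCC could therefore affect both the headline result and the choice of model.

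The missing DEXA site makes this harder to repair later. If the site is not captured, no later analysis can confirm that a spine film was compared with a spine value, or split the results properly by region.

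The single N raises a smaller question. The 0.05 precision is worked out for all subjects together, while a user of the tool will usually have one region's image in hand.

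**Working it through.** **1. The protocol's own figures.** Inputs from Methodology b): z = 1.96, precision c = 0.05, prevalence p = 0.373, sensitivity 0.911, specificity 0.689.

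- N_sen = 1.96² × 0.911 × 0.089 / (0.05² × 0.373) = 334.02, rounded up to 335.
- N_spec = 1.96² × 0.689 × 0.311 / (0.05² × 0.627) = 525.15, rounded up to 526.

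Both stated figures reproduce.

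**2. PCC over both regions.** The protocol gives neither the hip:spine mix nor the BMD gap, so both are assumptions here. Let r be the within-region PCC, f the share of one region, and d the difference in region means in within-region SDs. Assume predictions calibrated within each region, with the region means recovered. Put b = f(1−f)d². Then over both regions:

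- the variance of measured BMD is 1 + b;
- the variance of the predictions is r² + b;
- their covariance is r² + b.

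So pooled PCC = √[(r² + b)/(1 + b)]. For r = 0.60 and f = 0.5, b = d²/4:

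| d | b | (0.36 + b)/(1 + b) | Pooled PCC |
|---|---|---|---|
| 0 | 0 | 0.3600 | 0.60 |
| 0.5 | 0.0625 | 0.4225/1.0625 = 0.3976 | 0.63 |
| 1.0 | 0.25 | 0.61/1.25 = 0.4880 | 0.70 |
| 1.5 | 0.5625 | 0.9225/1.5625 = 0.5904 | 0.77 |

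A predictor that knows only the region (r = 0) scores 0.24, 0.45 or 0.60 at gaps of 0.5, 1.0 or 1.5. At an 80:20 mix, b = 0.16d² and the effect is smaller: r = 0.60 becomes √(0.40/1.04) = 0.62, √(0.52/1.16) = 0.67 or √(0.72/1.36) = 0.73. Centring measured and predicted BMD within region sets b to 0 and returns r.

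**3. Precision by region.** For n subjects the half-widths are 1.96 × √[0.911 × 0.089/(0.373n)] for sensitivity and 1.96 × √[0.689 × 0.311/(0.627n)] for specificity. With 600 subjects, one region each:

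| Subjects in region | Sensitivity | Specificity |
|---|---|---|
| 600 (whole sample) | 0.037 | 0.047 |
| 540 | 0.039 | 0.049 |
| 480 | 0.042 | 0.052 |
| 300 | 0.053 | 0.066 |
| 120 | 0.083 | 0.105 |
| 60 | 0.118 | 0.148 |

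By step 1, a region meets 0.05 for sensitivity with at least 335 subjects (335/600, about 56%) and for both measures with at least 526 (526/600, about 88%).

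**The case against.** The strongest reply is that pooling is inferred. Methodology f) does not say that the metrics are computed over both regions, and a table by site is something an analysis plan could supply. This stands in part: pooling is the natural reading of one model and one metric list, but it is not stated. An analysis plan could separate the results by region, but it could not restore a DEXA site that was never recorded.

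Second, the inflation depends on quantities outside the protocol. The gap, the mix and the calibration are assumed, and at a gap of 0 the effect is nil. This stands, and the finding is conditional on it. A reader might infer that the reported PCC will certainly be overstated; the protocol gives no figures to support that.

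Third, the effect is shown for PCC only. Pooled MAE is the weighted average of the regional MAEs and is not inflated by a region gap. No effect on AUPRC or accuracy has been shown. This also stands.

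Fourth, a reader might infer that the 0.05 precision fails in both regions. The protocol does not support that as a general statement. It never promises 0.05 per region. With an uneven split the larger region can meet it for sensitivity, or for both measures. Methodology c) collects all spine and hip images and nothing prevents a subject from contributing both, which would ease the shortfall. The 0.05 also concerns sensitivity and specificity, which are absent from the list in Methodology f); it was never a statement about PCC.

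**Conclusion.** The concern holds in a limited form. As written, the protocol neither records the region of the DEXA value nor separates hip from spine in evaluation, so the natural reading gives a PCC that mixes separation between regions with accuracy within them. Under calibrated predictions and an even mix, the rise from a within-region 0.60 is 0.03, 0.10 or 0.17 for gaps of 0.5, 1.0 or 1.5 SDs, and zero without a gap. It is smaller with an uneven mix.

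The precision point is a secondary clarification. The sample size arithmetic is right for the whole sample, but the plan does not secure 0.05 in each region. The half-widths of 0.053 and 0.066 assume an even split, one region per subject, and the protocol's own prevalence, sensitivity and specificity in each region.

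The point should be addressed before data collection closes, because the site field cannot be added by analysis alone.

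**What to change.** - In Methodology d), record the skeletal site of each DEXA value. In Methodology c), add region to the matching rule, so that each X-ray is paired with the DEXA value of the same region. The Questionnaire Form already asks the type of X-ray.
- In Methodology f), report MAE, PCC, AUPRC and accuracy separately for hip and spine as the main results. If an overall PCC is wanted, centre measured and predicted BMD within region first.
- In Methodology b), state that the 0.05 precision refers to sensitivity and specificity in the whole sample, and give the half-widths expected in each region for the anticipated split.

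**Cost:** one extra data field and some wording, with no additional patients. Per-region intervals will be wider, the reported PCC may be lower, and subjects whose X-ray and DEXA regions do not match may be lost. Guaranteeing 0.05 for both measures in each region would take 2 × 526 = 1,052 one-region subjects; the protocol does not promise that, and it is not asked for here.

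### Does establishing a balanced dataset before training and evaluation distort AUPRC and accuracy, or let copies of a patient cross the folds?

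*Protocol*

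**What the plan says.** Methodology e) Data Interpretation starts once data collection is complete. It describes an exploratory look at age, gender, menopausal status, cardiovascular disease and diabetes, and at how these correlate with BMD. The stated product is "the establishment of a balanced dataset that represents a wide spectrum of patient profiles". The next paragraph begins: "The refined dataset will serve as the foundation for training and evaluating our AI model".

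Methodology f) Statistical Analysis continues: "Upon finalizing the dataset, our statistical analysis will concentrate on evaluating". It names four metrics. Two measure agreement on the BMD scale (MAE and Pearson correlation). The other two are classification metrics: "Area Under the Precision-Recall Curve (AUPRC), and accuracy will be employed". For reliability it adds that "we will implement k-fold cross-validation techniques, providing a framework for evaluating our model across various subsets of data". Neither k nor the unit of splitting is given.

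Two earlier sections bear on the meaning of *balanced*. Methodology a) Study Population says: "The study will target a diverse demographic to account for the variability in bone health". Methodology b) Sample size calculation says: "we need the medical image samples to reflect the various osteoporosis, osteopenia and normal cases".

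**The concern.** Read in order, the text runs: collect, inspect the factors and their relation to BMD, balance, then train and evaluate on the result. No evaluation set is kept apart at the case mix as collected. If balancing is an operation on the data, three problems could follow.

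- **Case mix.** Accuracy and AUPRC both change with the proportion of osteoporosis cases even when the model does not. On a resampled set they would describe a mix chosen after the data had been inspected, and a reader could not tell which prevalence they apply to.
- **Leakage.** If cases were duplicated before the folds were drawn, the model could be tested on images it had been trained on, which would flatter every metric.
- **Precision.** If non-cases were discarded, specificity could miss the 5-point precision on which the sample size rests.

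This would matter for a tool that is meant to support osteoporosis screening and to guide whether a DEXA scan is warranted.

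**Working it through.** **Inputs from the protocol.** Methodology b): 95% confidence (z = 1.96), precision c = 0.05, p = 0.373, sensitivity 0.911, specificity 0.689, target N = 600. Introduction: risk of 43.2% in females and 30.3% in males. The Introduction describes the 37.3% as being at risk, so 0.373 is a planning value and not the known mix of the clinics.

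**Assumptions that are not in the protocol.** A binary endpoint (osteoporosis or not), an equal-variance binormal curve through the planning point, k = 5 or 10, and every balancing scheme below.

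**1. The protocol's own figures.**
- N_sen = 1.96² × 0.911 × 0.089 / (0.05² × 0.373) = 334.02, rounded up to 335.
- N_spec = 1.96² × 0.689 × 0.311 / (0.05² × 0.627) = 525.15, rounded up to 526.

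Both match the protocol.

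**2. Effect of case mix, with the classifier held fixed.**
- Accuracy = 0.911p + 0.689(1 − p) = 0.689 + 0.222p.
- AUPRC = ∫ p·r / [p·r + (1 − p)·Φ(z(r) − d)] dr over recall r from 0 to 1, with d = z(0.911) + z(0.689) = 1.347 + 0.493 = 1.840.

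| Evaluation mix | p | Accuracy | AUPRC |
|---|---|---|---|
| Planning value | 0.373 | 77.2% | 0.86 |
| Sexes 1:1, p = (0.432 + 0.303)/2 | 0.3675 | 77.1% | 0.85 |
| Three equal classes | 0.333 | 76.3% | 0.84 |
| Cases 50:50 | 0.500 | 80.0% | 0.90 |
| Collected mix, if 25% | 0.250 | 74.5% | 0.79 |
| Collected mix, if 60% | 0.600 | 82.2% | 0.93 |

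Balancing on sex, a factor that the protocol does list, changes accuracy by 0.222 × 0.0055 = 0.1 points. A larger change needs balancing on the outcome class. Its direction is then open: going to 50:50 from 25% adds 0.222 × 0.25 = 5.6 points of accuracy, while going there from 60% takes away 0.222 × 0.10 = 2.2 points.

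**3. Leakage.** Duplicates arise only if records are oversampled before the split. Undersampling and reweighting create none. Suppose 600 patients with 600 × 0.373 = 224 cases and 376 non-cases, and cases oversampled to 376 by adding 152 copies, so 752 rows in all.
- If 152 different cases are copied once each, 304 case rows have a twin. The chance that the twin falls in another fold is 1 − (752/k − 1)/751, which is 0.801 for k = 5 and 0.901 for k = 10. That affects 304 × 0.801 / 376 = 65% or 304 × 0.901 / 376 = 73% of the case rows.
- If the copies are drawn with replacement, simulation gives 61% or 66%.

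The effect would be serious, but the protocol describes no such scheme.

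**4. Precision.** Undersampling the same 600 to 224 + 224 would widen the specificity half-width from 1.96 × √(0.689 × 0.311 / 376) = 4.7 points to 1.96 × √(0.689 × 0.311 / 224) = 6.1 points. This takes the pool to be exactly 600. The protocol calls 600 a target, and its retrospective phase is to collect all spine and hip X-rays and BMD reports. Specificity is also not among the four metrics named in Methodology f).

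**5. What the wording supports.** The phrase in e) carries its own definition, a wide spectrum of patient profiles, and echoes the diverse demographic of a). The factors listed before it are covariates; outcome class is not among them. The sentence in b) asks that the sample reflect osteoporosis, osteopenia and normal cases, which is a request for presence and not for equal numbers. The model is described as regression-based, for which 50:50 class balancing is not the obvious step. *Refined* can refer to the exclusion of incomplete or poor-quality records in a) and to the homogenization step in the Flow Chart.

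**The case for a change.** The strongest reply is that this is something the protocol commits to, and not merely something it leaves out. Balancing comes after collection, so it cannot be a recruitment target. Looking at data does not balance them, so some operation seems implied. The product is called refined and is assigned to evaluation as well as training. An analysis plan that evaluated on unaltered data would then depart from the natural reading of e). Clarifying the term would take a sentence or two and no extra patients.

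Part of this stands. The word is loose, the order of the text does put it before cross-validation, and the dependence of accuracy and AUPRC on case mix is correct arithmetic. But the step from a loose word to a faulty procedure has to be supplied by the reader. Sections e) and f) do not say that any resampling precedes the fold split. Section f) includes a comparison of training methodologies, so class handling inside the training folds is compatible with the text. An analyst who took *balanced* as broad coverage, or who resampled only within training folds, would contradict nothing in the protocol.

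**Conclusion.** The concern does not hold as an error in the plan. Under the reading that the wording favours, no patient is dropped, duplicated or reweighted, and the metrics apply to the patients collected. The one covariate scheme that can be computed from the protocol's figures moves accuracy by about 0.1 points. The larger effects (80.0% against 77.2% accuracy, 61–73% of case rows with a copy in another fold, a 6.1-point specificity half-width) each need an outcome-balancing scheme that the protocol does not contain. They rest further on a binary endpoint and, as applicable, on the binormal curve, an assumed k or a pool fixed at 600.

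What remains is an undefined term and unspecified fold handling, both of which a statistical analysis plan commonly settles; that plan is not at hand. The gain from changing the protocol is also uncertain. The sign of any shift depends on a prevalence not yet observed. Evaluating at the collected mix would not yield screening performance either, because inclusion requires both an X-ray and a DEXA result. When the analysis is written up, the analyst would do well to split by patient, keep any resampling inside the training folds and state the prevalence beside accuracy and AUPRC. That is ordinary practice and needs no amendment.
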